# 1 TRIAL BACKGROUND INFORMATION AND RATIONALE

## 1.1 Presentation and impact of Lichen Sclerosus

Vulval Lichen Sclerosus (LS) is a chronic inflammatory condition, with incidence peaks in childhood and post-menopause [1, 2]. Reported prevalence is up to 3%, affecting around 1 million women in the UK. Inflammation causes whitening of vulval tissue, bleeding under the skin, texture change and cuts. Patients report itching, pain (particularly during sex) and discomfort in daily activities [2]. Paediatric vulval LS accounts for up to 15% of cases [3-5]. In adults, inflammation leads to scarring which can narrow the vaginal entrance, bury the clitoris and resorb/fuse the labia minora. Untreated LS causes progressive loss of vulval architecture. Scarring may occur early in the disease [6, 7] and is irreversible without surgery [8]. LS persisting beyond puberty can prevent normal vulval anatomical development [4]. LS also occurs in males, but prevalence is believed to be less. LS is associated with risk of vulval intraepithelial neoplasia (VIN, a pre-malignant condition) and vulval squamous cell cancer (SCC, an invasive malignancy). Rates of vulval SCC with LS are 20 times higher than in the general population [9] with higher mortality than vulval SCC without LS [10].

The impact of LS is considerable due to the intimate and 'taboo' nature of the problem. LS affects psycho-social and sexual functioning and leads to embarrassment, isolation and relationship breakdown/difficulty in forming new relationships [11, 12]. A national survey of 325 women with a vulval health disorder reported that women with LS were twice as likely to have suffered with depression and over one-fifth had contemplated self-harm or suicide as a result of their condition [13].

## 1.2 Current management of LS

Treatment goals are to control symptoms, prevent scarring and reduce the risk of cancer. First-line therapy with a superpotent topical corticosteroid (TCS) applied daily for three months, combined with a soap substitute and barrier emollient to protect from irritants [14] achieves normalisation of skin colour/texture and resolution of symptoms in 70% patients [7]. However, LS is a relapsing-remitting condition and evidence to inform maintenance of remission/prevention of progression is poor. In many girls, the disease remits at puberty, but this cannot be assumed, and some studies describe a more chronic course where resolution does not always occur and continued treatment is necessary [15, 16]. A critically appraised topic has shown that 37% of girls have symptoms that persist past the first 3 months of treatment, 67% who were in remission recur after 1 year and 55% recur after 4 years [17].

It is important to note that LS can also affect boys and men, but there are differences in the management of male LS as circumcision is believed to be curative and long-term maintenance is usually not required. This protocol, therefore, is only in reference to women and girls with vulval LS.

## 1.3 Evidence for long term treatment of LS

Long term LS management strategies are not backed up by strong randomised controlled trial (RCT) evidence. UK guidelines are based on expert consensus [18], a few observational studies [14] and a small number of RCTs with, most assessed as low quality of evidence. A single armed, prospective study of patients with vulval LS in clinical and histological remission suggests 50% will

have relapsed after 16 months and 84% after 4 years [19]. UK guidelines state that there is no evidence for an optimal maintenance regimen [20] and European guidelines reiterate that 'maintenance' treatment is a matter of debate [21]. A recent commentary noted variation in ongoing management [22] and an Australasian consensus statement advises long term individualised proactive maintenance therapy [23].

#### **1.4 Rationale of the trial**

The trial will address two priorities from the 2018 Lichen Sclerosus Priority Setting Partnership [24]: a) What is the best way to prevent and manage anatomical changes caused by LS? b) Is it necessary to continue treatment for patients with LS who do not have any symptoms and/or signs of disease activity?

There are no robust long term RCTs to compare proactive against reactive TCS therapy for LS. An observational study [25] suggests symptoms and scarring are reduced by proactive therapy. Another small study (n=27) reports 60% of patients using only emollients will have a relapse compared with none using proactive TCS over one year [26].

Alternative topical treatment options are either unsuitable or ineffective [21, 23]. Topical calcineurin inhibitors pose theoretical increased risk of cancer due to their immunosuppressant effects on T cells. Topical retinoids are irritant to vulval skin, furthermore retinoids are teratogenic and therefore unsuitable for large proportion of LS sufferers. Topical testosterone has not been found to be effective. At present, there are no other known topical agents on the horizon for first line treatment of LS. As a result, TCS, which are inexpensive, effective and well understood, remain the mainstay of LS treatment. Optimising their usage and standardising advice given to patients is important.

The PEARLS Trial will compare reactive and proactive TCS maintenance strategies in a superiority trial of proactive over reactive treatment. The trial recruitment will be from primary and secondary care, including both women and girls  $\geq 5$  years of age with vulval LS. Due to differences in management and outcomes between male and female patients and reduced prevalence of LS in males, only female patients will be included. Paediatric patients are included, due to even greater paucity of evidence for this subset. There is a clear peak of incidence in girls aged four to six years old, which represents 7–15% of all vulvar lichen sclerosus cases [27]. The only published randomised control trial with paediatric patients enrolled only a handful of children and reported their data together with adult participants, making it impossible to draw any conclusions about the prepubertal patients [28]. Follow-up will be for 2 years to assess for scarring, with optional consent obtained for longer term outcomes and economic modelling (separate funding to be sought if appropriate).

#### **1.5 Overall risk assessment of the trial**

PEARLS is a pragmatic trial and trial participants in both intervention and comparator group will receive commonly prescribed topical corticosteroids (TCSs), which is tailored for the participant. The only difference between the treatment groups is the treatment regimen/strategy. TCSs are licensed products. Their use for lichen sclerosus has been an established practice in healthcare. It is therefore considered that participants in the treatment group ('proactive' group)

are not at a higher risk than those in the comparator group ('reactive' group). Given that all TCSs are licenced treatments, used as off-label basis in routine practice for the same indication, the trial has been considered to be a phase IV trial and is consistent with risk type category A. Although TCSs can be safely applied to the whole body in a single dose with minimal risk of adverse reactions, there is however a risk of adverse reactions following long-term use of topical corticosteroid on localised areas of skin (e.g. skin thinning, telangiectasia). These will be monitored during clinical examination at follow-up visits (or at an unscheduled trial visit, as necessary). There is no additional risk identified in children with the use of TCSs. Adverse reactions used in the paediatric population will be monitored in the same way as in adults. Safety reporting procedure is described in section 11.

## 2 DETAILS OF INVESTIGATIONAL MEDICINAL PRODUCT(S) (IMP)

### 2.1 Description

Participants will be randomised to one of two treatment strategies:

**Intervention group:** Potent or superpotent topical corticosteroid (TCS) to be applied on two non-consecutive days per week even in the absence of symptoms (proactive).

**Comparator group:** Potent or superpotent topical corticosteroid (TCS) to be applied as required to treat a LS flare (reactive).

More details on the treatment strategies are described in Table 6. Intervention vs comparator group. Choice of TCS will be according to the patient's usual care and the trial will test TCS as a class defined by their Anatomical Therapeutic Chemical (ATC) classification numbers D07AC and D07AD (for potent and superpotent respectively). As this is a pragmatic trial, we will test the strategy of proactive vs reactive treatment using the potency of topical corticosteroid recommended by the treating clinician (potent or superpotent). There are several generic names available for these prescribed TCSs and all available brands and forms can be prescribed. The examples of the most commonly prescribed brands/products of the TCS class are listed below (for details see Table 1):

- Dermovate ointment - superpotent TCS
- Elocon® 0.1% w/w ointment - potent TCS

Table 1. Potent and superpotent TCSs description

Name of exemplar product	International Non-Proprietary Name (INN)	Potency	Chemical name or CAS number	Formulation	Excipients	ATC code	Chemical and pharmacological properties	Manufacturer and MA (Marketing Authorisation) number
Dermovate ointment	Clobetasol 17-propionate 0.05375% w/w	Superpotent	25122-46-7	Ointment	Propylene glycol, Sorbitan sesquioleate, White soft paraffin.	D07AD01	Pharmacotherapeutic group: Corticosteroids, very potent, dermatological preparations (group IV). Topical anti-inflammatory activity. The major effect on skin is a non-specific anti-inflammatory response, partially due to vasoconstriction and decrease in collagen synthesis.	Manufacturer: GlaxoSmithKline UK  MA number: PL 10949/0028
Elocon® 0.1% w/w Ointment	Mometasone furoate 0.1% w/w	Potent	83919-23-7	Ointment	Hexylene glycol, Phosphoric acid, Propylene glycol stearate, White beeswax, White soft paraffin, Purified water.	D07AC13	Pharmacotherapeutic group: Corticoids, potent (group III) Exhibits marked anti-inflammatory activity and marked anti-psoriatic activity in standard animal predictive models.	Organon Pharma (UK) Limited, UK  MA number: PL 00025/0578

## 2.2 Manufacture

The IMPs to be used in this trial will be manufactured by the MA holder as they are to be obtained from standard pharmacy stock.

## 2.3 Packaging and labelling

In accordance with the Medicines and Healthcare products Regulatory Agency (MHRA) risk-adapted approach to the management of clinical trials of investigational medicinal products, and the pragmatic nature of the trial, this trial will not require trial specific labelling [29]. This is considered a Type A trial, as all LS treatments being used in this trial are established treatments with well documented safety profiles. The TCSs used in the trial are “off the shelf” and are widely prescribed in standard care for patients with LS. Their use is already established practice for the treatment of LS and supported by published guidelines. This trial is merely exploring comparison of effects of different treatment strategies used in patients with LS. No new side effects are anticipated and the risk to patients is therefore low.

## 2.4 Storage, dispensing and return

IMPs will be stored in accordance with the standard conditions for these products whilst in the community pharmacies, and as per the instructions on the product when in the participant’s home. Dispensing will be via community pharmacies as per current practice. Returns will not be made and products should be disposed of in accordance with the accompanying, standard, product instructions.

## 2.5 Placebo/comparator

No placebo is being used in this trial. The comparator is a strategy of reactive treatment to manage disease flares, as detailed in sections 2.1 and 8.

## 2.6 Known Side Effects

Known adverse reactions to TCSs include: infection, folliculitis, paraesthesia, burning sensation, contact dermatitis, skin hypopigmentation, hypertrichosis, skin striae, acneiform dermatitis, skin atrophy, pruritus and application site pain, according to the Summary of Product Characteristics (SmPC).

TCSs are used to treat a very wide range of inflammatory skin conditions, including common conditions such as eczema, psoriasis, vitiligo as well as LS. The risk of adverse effects for potent or superpotent TCSs (such as used in this trial) is modest, but it is widely acknowledged that the fear of adverse effects is usually disproportionately high, given the relative infrequency with which such adverse effects are observed. Despite the ubiquity of topical corticosteroids in dermatological therapeutic practice, there is surprisingly little evidence to quantify the risk of adverse effects accurately. Guidelines often suggest that potent/superpotent TCSs should be used only under close clinical supervision, particularly when used in children on anatomical sites where the skin is thinner and therefore more prone to adverse effects such as atrophy.

## 2.7 Reference Safety Information:

There are number of TCS products available on the market and all available brands and forms can be prescribed to participants. The safety information of two of the most commonly used TCSs, as listed in Table 1, are described in corresponding exemplar SmPCs and will act as the reference safety information for the trial:

- Superpotent TCS - Dermovate ointment - SmPC dated 16-Aug-2023, section 4.8
- Potent TCS - Elocon® 0.1% w/w Ointment - SmPC dated 20 April 2023, section 4.8

## 3 TRIAL OBJECTIVES AND PURPOSE

### 3.1 Purpose

To compare the clinical and cost effectiveness of a twice weekly topical corticosteroid maintenance strategy (proactive therapy) with as required treatment (reactive therapy) in the management of vulval LS.

### 3.2 Primary objectives

Compare the effectiveness of proactive versus reactive strategies for using topical corticosteroids on the number of flares within 12 months, in people aged  $\geq 5$  years with vulval LS.

### 3.3 Secondary objectives

1. Assess the effectiveness of proactive versus reactive use of TCSs over 24 months in reducing disease progression.
2. Assess the clinical effectiveness of proactive versus reactive strategies for the management of vulval LS for up to 24 months.
3. Assess the safety of using potent and superpotent TCSs in the vulval area over 24 months.
4. Assess the cost-effectiveness of the two treatment strategies.
5. Understand the acceptability of reactive and proactive long-term treatment strategies and the barriers and facilitators to continuing with prescribed treatment.

Trial objectives and outcome measures as mapped in Table 2.

Table 2. Mapped objectives and outcome measures

Objective	Outcome Measure	Outcome Time Point	Method
Primary objective			
Compare the effectiveness of proactive versus reactive strategies for using topical corticosteroids on the number of flares within 12 months, in people aged $\geq 5$ years with vulval Lichen Sclerosis	Number of flares	Over 12 months	Text/app/email reminders every two weeks for 12 months Participant reported
Secondary objectives			
1. Assess the effectiveness of proactive versus reactive use of TCS over 24 months in reducing disease progression	Scarring	At 12 and 24 months	Clinical assessment comparing to baseline photographs, if consent given, or comparing to baseline clinical assessment diagram if consent for photographs not obtained.
	VASS	At 12 and 24 months	Clinical assessment
	Development of VIN or vulval SCC	Over 24 months	Clinical assessment/medical notes
2. Assess the clinical effectiveness of proactive versus reactive strategies for the management of vulval Lichen Sclerosis for up to 24 months	Global clinical severity assessment	At 3, 6, 12, 18 and 24 months	Clinical assessment
	Sexual function	At 12 and 24 months	Participant reported
	Time to first flare	At 1 st flare over 12 months	Text/app/email reminders every two weeks for 12 months Participant reported

Objective	Outcome Measure	Outcome Time Point	Method
	Condition specific QoL CDLQI (adolescents and children) and VQLI (adults)	At 3, 6, 12, 18 and 24 months	Questionnaire Participant reported
	Generic utility instrument measured by EQ-5D-5L (adolescents and adults) and CHU-9 (children)	At 3, 6, 12, 18 and 24 months	Questionnaire Participant reported
3. Assess the safety of using potent and superpotent TCSs in the vulval area over 24 months	Adverse events	For the duration of participation	Participant reported/clinical assessment/medical notes
4. Assess the cost-effectiveness of the two treatment strategies.	Resource use	At 3, 6, 12, 18 and 24 months	Questionnaire Participant reported
5. Understand the acceptability of reactive and proactive long-term treatment strategies and the barriers and facilitators to continuing with prescribed treatment	Adherence to treatment	At 3, 6, 12, 18 and 24 months	Questionnaire Participant reported
	Acceptability of treatment	At 12 24 months	Questionnaire Participant reported
	Barriers and facilitators	At 12 months	Qualitative interviews

## 4 TRIAL DESIGN

### 4.1 Trial configuration

PEARLS is a 2-arm, parallel-group, individually randomised, open label assessor-blinded, multicentre, superiority trial with an internal pilot phase.

## 4.2 Trial flowchart

[figure not shown]

Figure 1. Trial flowchart

\*For participant identification and screening pathways please refer to section 7.2

\*\*See details in section 13

### 4.3 Primary endpoint

Number of flares over 12 months. Flare is defined as worsening of symptoms requiring increased application of TCSs as reported by participants via two weekly reminders.

### 4.4 Secondary endpoint

For the purposes of recording outcomes, age categories are divided into:

- A. Children (5 - <12 years)
- B. Adolescents (12 - <16 years)
- C. Adults (16 years and over).

### Clinical effectiveness

- Progression of scarring assessed by blinded assessor at 12 and 24 months by comparing post randomisation to baseline photographs (if participant consented), or assessed clinically if consent has not been given for photographs:
  - Adults: scarring worsened (yes/no)
  - Children and adolescents: failure of normal vulval development (clinical assessment) and/or evidence of scarring (yes/no).
- Vulvar Architectural Severity Scale at 12 and 24 months post randomisation (VASS) [30].
- Time to first flare.
- Global clinical severity assessment of LS (5-point ordinal scale) at 3, 6, 12, 18 & 24 months, plus assessed by blinded assessor at 12 and 24 months.
- Condition specific QoL at 3, 6, 12, 18 & 24 months using:
  - Vulvar Quality Life Index (VQLI) (adults) [31]
  - Children's Dermatology Life Quality Index (CDLQI) (adolescents and children) [32].
- Sexual function (adults only) using Female Sexual Function Index [33] at 12 & 24 Months.

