### 5.1 Maintenance of randomisation codes and procedures for breaking code

The research staff randomising a participant won't be blinded to the allocation due to the nature of the treatment.

The outcomes to which an assessor will be blinded to treatment allocation will be scarring, assessed at 12 and 24 months. Global clinical severity will normally be reported by the site unblinded clinician at all time points but additionally it will be assessed by the blinded assessor at 12 and 24 months. The blinded assessor will be someone that is deemed by the PI as adequately qualified (and recorded on the delegation log) to examine and identify changes in participants with vulval LS. They will not be involved in any other trial activities. A blinded assessor will compare changes at 12 and 24 months against baseline photos or clinical assessment diagram. Where a blinded assessor is not available at the time of clinical assessment, assessment will be made subsequently by review either of the photos taken during the assessment or by comparison with the clinical diagram, and record findings. Revealing the treatment strategy allocation to the assessor should not be necessary as both involve topical steroids. However, in the unlikely scenario that assessors identify safety concerns, such as vulval cancer/pre-cancer, they will report to the site Principal Investigator (PI), who is unblinded, and who will inform NCTU as per the NCTU standard process.

The trial statisticians and Trial Steering Committee (TSC) members will be blinded to participant group allocations. An unblinded independent NCTU statistician will produce closed reports for the Data Monitoring Committee (DMC). No emergency unblinding processes are necessary. The Table 4 below describes which trial staff will be blinded/unblinded to the treatment allocation.

Table 4. Blinding status of the PEARLS trial staff

	Blinding status	Comments
Participant	Not blinded	Not practical due to trial design
Principal Investigator and other site staff	Not blinded	Not practical due to trial design
Clinical assessor at site	Blinded assessor	Scarring and global clinical severity assessment at 12 and 24 months
	Unblinded assessor	Global clinical severity at all time points and development of VIN or vulval SCC at 24 months
Chief Investigator	Blinded	The Chief Investigator will remain blinded to treatment allocation with an exception of participants recruited at their site.

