### 7.4 Eligibility criteria

#### 7.4.1 Inclusion criteria

1. Clinical or biopsy confirmed diagnosis of vulval LS
2. Currently controlled disease (asymptomatic with minimal clinical evidence of active disease) at baseline
3. Age  $\geq 5$  years
4. Able to give consent/child assent plus parental consent

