### Baseline

#### Visit 1

(at baseline)

- Informed consent
- Eligibility check and confirmation
- Contact details
- Collection of baseline data:
  - Concomitant medication (relevant to condition) and relevant medical history
  - Demographic information
  - Clinician global severity assessment
  - Scarring assessment (VASS, clinical examination)
  - Vulval development and scarring (in adolescents and children)
  - Condition specific QoL (VQLI or CDQLI)
  - Health related QoL assessed by EQ-5D-5L in adolescents/adults and CHU-9D in children
  - Bespoke resource use questionnaire and healthcare questionnaire
- Clinical photographs, or clinical diagram if consent for photographs not taken
- Randomisation

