#### Clinical photographs

Photographs will be taken at baseline for patients who consent to this, to assess scarring. Photographs will not be a mandatory requirement as some patients are hesitant due to the intimate nature of LS. Parents of children with LS are less likely to consent to photographs. Photographs taken up to 1 month prior to baseline appointment can be accepted, if the patient had no active disease during this period. If a photograph is not taken, clinicians will be asked to document a detailed clinical diagram (using a predefined schematic diagram) for comparison. Images taken at the baseline will remain in participant's medical notes and will not be sent to NCTU. Subsequent clinical examinations will assess changes against the baseline photo/diagram. Blinded assessments of scarring (or failure of normal anatomical development as appropriate) will be assessed at 12 and 24 months comparing to baseline clinical photographs.

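### The under-16 scarring item records presence rather than progression, and the fallback when no blinded assessor attends leaves ratings without photographs unblinded at source

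*Protocol*

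**What the plan says.** **The outcome.** Section 4.4 (Clinical effectiveness) describes "Progression of scarring assessed by blinded assessor at 12 and 24 months by comparing post randomisation to baseline photographs", or clinically where there is no consent to photographs. Two response items follow, and the synopsis repeats them:

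- "Adults: scarring worsened (yes/no")
- "Children and adolescents: failure of normal vulval development (clinical assessment) and/or evidence of scarring (yes/no")

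**Who enters.** The disease-status criterion in section 7.4.1 is "Currently controlled disease (asymptomatic with minimal clinical evidence of active disease) at baseline". It concerns symptoms and activity. No exclusion criterion in section 7.4.2 mentions scarring. Section 1.1 states: "Scarring may occur early in the disease [6, 7] and is irreversible without surgery [8"].

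**Baseline record.** Visit 1 in section 8.1 includes "Vulval development and scarring (in adolescents and children"), so the starting state of every under-16 is meant to be on file.

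**The fallback.** Where a blinded assessor is not available at the visit, section 5.1 says that "assessment will be made subsequently by review either of the photos taken during the assessment or by comparison with the clinical diagram".

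**Photographs and diagrams.** Section 8.1 (Clinical photographs) says: "Photographs will be taken at baseline for patients who consent to this, to assess scarring". If none is taken, clinicians complete a schematic diagram for comparison. Table 3 also places photographs at baseline only, and the lists for visits 4 and 6 contain no photograph.

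**The concern.** Two features could stop this outcome from delivering blinded progression in part of the sample.

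(a) The adult item asks about change and the under-16 item asks about presence. An adult with stable old scarring is scored no; a girl with the same history can be scored yes. Such events occur equally in both arms and carry no information about treatment, so they dilute any difference in under-16s. The protocol itself describes evidence in this age group as especially scarce.

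(b) Participants and site staff know the allocation, so the protection against assessment bias is that the rater does not. If the blinded rater never sees the vulva at 12 or 24 months, and has no photograph of it, the rating depends on what someone else recorded. If that person knew the allocation, blinding the rater does not remove the bias.

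Scarring is one of three measures that Table 2 maps to secondary objective 1, and it is the stated reason for two-year follow-up.

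**Working it through.** The protocol gives no rate or sample size for scarring; its 320 (400 randomised) concerns flares. There is no figure of the plan's own to reproduce here.

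**(a) State against change**

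Inputs from the protocol: the item wording (4.4 and synopsis), no exclusion for scarring (7.4), scarring irreversible without surgery (1.1). Assumed: b, the share of under-16s already scarred at entry, and p, the true progression risk in each arm.

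If every girl scarred at entry is scored yes:

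- observed risk = b + (1 − b)p
- observed difference = (1 − b)(p_reactive − p_proactive)

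The shrinkage factor 1 − b holds for any p. With assumed true risks of 20% and 10%:

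| b | Reactive | Proactive | Difference | Risk ratio (reactive/proactive) |
|---|---|---|---|---|
| 0 | 20% | 10% | 10 points | 2.00 |
| 0.1 | 28% | 19% | 9 points | 1.47 |
| 0.3 | 44% | 37% | 7 points | 1.19 |
| 0.5 | 60% | 55% | 5 points | 1.09 |

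With assumed risks of 10% and 5% and b = 0.3: 0.30 + 0.70 × 0.10 = 37.0% and 0.30 + 0.70 × 0.05 = 33.5%. The difference falls from 5.0 to 3.5 points, and the ratio (proactive/reactive) moves from 0.50 to 0.91. A definition based on change restores the b = 0 row, provided that girls already scarred progress at the same rate as the others.

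The dilution is confined to under-16s. Section 1.1 puts paediatric cases at up to 15%. If under-16s were 15% of the sample and ages were pooled (both assumptions), the second set of inputs gives 0.85 × 0.10 + 0.15 × 0.370 = 14.05% and 0.85 × 0.05 + 0.15 × 0.335 = 9.28%, ratio 0.66 against a true 0.50. At b = 0.1 the ratio is 0.57.

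**(b) Where the fallback rating gets its information**

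1. Default at visits 4 and 6: scarring (VASS and examination) by the blinded assessor, in person. Blinded.
2. Assessor absent, visit photographs available: compared with baseline photographs by a blinded reader. Blinded, but the visit lists and Table 3 do not schedule these photographs. Table 5 points the other way: it lists clinical photographs among data still collected after some forms of withdrawal, which must be after baseline. The Table 7 row naming optional photographs is marked at 12 and 24 months, though its footnote describes clinical assessment against baseline images.
3. Assessor absent, no visit photographs: comparison with the clinical diagram. The only diagram described is the baseline one, which says nothing about month 12 or 24. Any follow-up record must come from someone at the visit, and Table 4 lists the principal investigator and other site staff as not blinded.

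The size of route 3 is not given. If 20–50% of visits lacked an assessor, 30–50% of participants lacked photographs, and the two were independent (all assumed), it would be 0.20 × 0.30 = 6% to 0.50 × 0.50 = 25% of ratings. Section 8.1 says parents are less likely to consent to photographs, so children are the likeliest to be on this route. The separate visit line on vulval development and scarring in under-16s also carries no blinded-assessor label at visits 4 and 6.

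**The case against.** The strongest reply to (a) is that the under-16 item sits beneath a stem about progression, and that comparison with baseline is stated repeatedly without an age limit: in Table 2, section 5.1, section 8.1 (which names failure of normal development expressly) and the Table 7 footnote. That stands in part. A reader might infer that the protocol instructs raters to count pre-existing scarring; it does not. The text conflicts with itself, and raters following the response item could reasonably differ from raters following the stem.

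On (b), direct examination by the blinded assessor is the default, photo pairs read blind remain blind, and the baseline diagram is listed before randomisation at visit 1, so knowledge of allocation cannot colour it. All of that stands. The protocol also never says that an unblinded clinician draws a follow-up diagram. That is an inference, made because no other source of follow-up information is described.

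A sensitivity analysis is ordinarily detail for the statistical analysis plan, which is not shown. But no later plan can recover change if sites recorded presence, or separate the rating routes if the route was never captured. VASS is a further structural outcome with a baseline value and blinded follow-up assessment. It softens the loss without repairing this item.

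**Conclusion.** Both defects hold in limited form. (a) The under-16 item conflicts with its own stem. Scored as written, it shrinks the risk difference in under-16s by 1 − b. The factor is exact if everyone scarred at entry is scored yes; b and the progression risks are not in the protocol, so the tabulated values are illustrations only. (b) Ratings made with no blinded assessor present and no visit photographs are not blinded at source. This rests on the inference from Table 4, and the size of the subset is unknown.

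It would be tempting to conclude that the scarring outcome as a whole does not measure blinded progression. The documents do not support that: an adult examined in person by the blinded assessor is scored on exactly that. Nor do they rank scarring above VASS or VIN/SCC within secondary objective 1. The primary outcome is untouched. The matter should be corrected because it affects a secondary outcome of evident importance and costs little to repair.

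**What to change.** (a) Reword the under-16 item in section 4.4 and the synopsis as: new or worsened scarring, or failure of normal vulval development, relative to baseline (yes/no). The baseline record is already collected at visit 1.

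(b) Reconcile sections 4.4, 5.1 and 8.1 and Tables 3, 5 and 7 by listing photographs at 12 and 24 months for participants who consented to photographs. Add one e-CRF field for the rating mode (in person, photo pair, diagram only). Do not describe diagram-only ratings as blinded, and plan a sensitivity analysis that excludes them.

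Cost: a wording amendment, one e-CRF field, one additional analysis, a follow-up photograph in people who have already agreed to photographs, and slightly fewer ratings in the strictly blinded analysis.
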